3. PATIENT ELIGIBILITY AND ENTRY CRITERIA

IMPORTANT NOTE: The eligibility criteria listed below are interpreted literally and cannot be waived. All clinical and laboratory data required for determining eligibility of a patient enrolled on this trial must be available in patient's medical/research records which will serve as a source for verification at the time of the audit.

This protocol is open to both males and females of all races and ethnicities. Participants must meet the following criteria on screening examination to be eligible to participate in the study. See Inclusion Criteria regarding specific eligibility requirements for female and male patients of childbearing or child-fathering potential, respectively.

All clinical and laboratory studies to determine eligibility must be performed within 14 days prior to enrollment unless otherwise indicated. Laboratory values used to assess eligibility must be no older than 14 days at the start of therapy. Laboratory tests do not need to be repeated if therapy starts within 14 days of obtaining labs to assess eligibility, with the exception of the pregnancy test, which must be performed within 7 days of starting treatment. Imaging studies must be obtained within 4 weeks (28 days) prior to enrollment and starting treatment. For OPG patients, functional ophthalmology assessments must be performed within 4 weeks (28 days) prior to enrollment and starting treatment.

3.1. Inclusion Criteria

- 1) Age: Patients must be less than 22 years at the time of enrollment; there is no lower age limit.
- 2) All participants must have an identified pathogenetic constitutional *NF1* mutation OR the clinical diagnosis of NF1 using the NIH Consensus Conference criteria (**See Appendix 1**).

- 3) Diagnosis: LGG (WHO Grade 1 and 2) of the brain and spinal cord are eligible. Histologic confirmation of tumor is not necessary in the presence of consistent clinical and radiographic findings. Biopsy for histologic diagnosis is required if there is clinical suspicion for a high-grade tumor; special attention is recommended in older adolescents or young adults to the potential for malignant transformation. Patients with metastatic disease are eligible.
- 4) Patients must meet at least one of the following criteria for progression or recurrence of a previously treated target tumor:
 - a. Progression or recurrence on MRI.
 - b. New or worsening neurologic symptoms attributable to the target tumor.
 - c. For patients with OPG: visual worsening, defined as worsening of visual acuity (VA) or visual fields (VF) documented within the past year by examination or history, attributable to tumor.
- 5) Measurable Disease: Patients must have two-dimensional measurable tumor $>1\text{cm}^2$.
- 6) Prior Therapy: Patients must have had at least one prior medical treatment for the target LGG.
- 7) Performance Level: Patients must have a performance status of equal or $>$ than 50 using Karnofsky for patients equal or \geq 16 years of age and Lansky for patients $<$ 16 years of age. **See Appendix 2 for scale.**
- 8) Patients must have recovered to grade ≤ 1 from any acute toxicities from all prior treatments. to enroll on this study and meet time restrictions from end of prior therapy as defined below:
 - a. Myelosuppressive chemotherapy: must have received the last dose of myelosuppressive therapy at least 4 weeks prior to study registration, or at least 6 weeks if nitrosourea.
 - b. Investigational/biological agent: Patient must have received the last dose of other investigational, immunotherapy, or biological agent $>$ 14 days prior to study registration or at least 5 half-lives, whichever is greater. Bevacizumab last dose $>$ 36 days prior to enrollment.
 - c. Radiation therapy: Patients SHOULD NOT have received prior irradiation.
 - d. Study specific limitations on prior therapy: There is no limit on the number of prior treatment regimens.
 - e. Growth factor(s): Must not have received any hematopoietic growth factors within 7 days of study entry or $>$ 14 days if pegylated GCSF is used.
 - f. Prior surgery: At the time of enrollment, must be \geq 3 weeks from prior major surgery such as craniotomy, orthopedic surgery, abdominal surgery or \geq 1 week from minor surgery

and completely recovered. Port or central line placement is not considered a major surgery.

9) Organ Function Requirements:

All patients must have adequate organ function defined as:

9.1 Hematologic Function:

- a. Hemoglobin: ≥ 8.0 gm/dL (may transfuse PRBCs)
- b. ANC: $\geq 750/\text{mm}^3$. Must be at least 7 days after last dose of growth factor or > 14 days since last dose of pegylated GCSF
- c. Platelet Count: $\geq 75,000/\text{mm}^3$ (transfusion independent; ≥ 7 days from last transfusion)

9.2 Renal Function: Serum creatinine which is less than 1.5 times ULN for age (as per the table below) or GFR > 70 ml/min/1.73m²

Table 3: Renal Function Normal for Age

Age	Maximum Serum Creatinine (mg/dL)	
	Male	Female
1 month to < 6 months	0.4	0.4
6 months to < 1 year	0.5	0.5
1 to < 2 years	0.6	0.6
2 to < 6 years	0.8	0.8
6 to < 10 years	1	1
10 to < 13 years	1.2	1.2
13 to < 16 years	1.5	1.4
≥ 16 years	1.7	1.4

9.3 Liver Function:

- a. Total bilirubin $\leq 1.5 \times$ ULN (Children with diagnosis of Gilbert's Syndrome will be allowed on the study regardless of their total and indirect bilirubin levels as long as the direct bilirubin is less than 3.1 mg/dL.)
- b. SGPT (ALT) $\leq 5 \times$ ULN
- c. SGOT (AST) $\leq 5 \times$ ULN

9.4 Pulmonary Function:

No evidence of dyspnea at rest, and a pulse oximetry $\geq 92\%$.

9.5 Reproductive Function:

Female patients of childbearing potential must have a negative serum or urine pregnancy test within 7 days prior to the first dose of poly-ICLC. Patient must not be pregnant or breast-feeding. Patients of childbearing or child-fathering potential must be willing to use a medically acceptable form of birth control, including abstinence, while being treated on this study and for 90 days following cessation of treatment.

- 10) Patient is able to start treatment within 7 days after enrollment.
- 11) Patients with neurological deficits must be stable for a minimum of 1 week prior to enrollment.
- 12) Patients are only eligible if complete resection of the LGG with acceptable morbidity is not feasible or if a patient with a surgical option refuses surgery.
- 13) Patients and/or parents/legal guardians must provide written informed consent and agree that they will comply with the study.

3.2. Exclusion Criteria

1. Prior radiation treatment for the low-grade glioma.
2. Prior exposure to poly-ICLC.
3. Patients currently receiving other anti-tumor therapy or experimental therapy (targeted agents, chemotherapy radiation).
4. Patients with a current or prior diagnosis of malignant glioma (WHO grade III or IV).
5. Patients with a prior diagnosis of malignant peripheral nerve sheath tumor or other malignancy requiring treatment in the last 48 months.
6. Patients may not have fever (≥ 38.50 C) within 3 days of enrollment.
7. Patients who, in the opinion of the investigator, may not be able to comply with the safety monitoring requirements of the study.
8. Active auto-immune illness.
9. Pregnant or lactating females.
10. Sexually active patients of reproductive potential who have not agreed to use an effective contraceptive method for the duration of their study participation and for 90 days after stopping study therapy are not eligible.
11. Severe unresolved infection that requires systemic IV antibiotics.
12. Patients with any significant medical illnesses that in the investigator's opinion cannot be adequately controlled with appropriate therapy or would compromise the patient's ability to tolerate this therapy.
13. Uncontrolled intercurrent illness including, but not limited to, ongoing or active infection, symptomatic congestive heart failure, unstable angina pectoris, cardiac arrhythmia, impaired gastrointestinal function, or psychiatric illness/social situations that would limit compliance with study requirements.
14. Patients requiring high doses of steroids. Patients may not be on immunosuppressive therapy, including corticosteroids (with the exception of physiologic replacement, defined as ≤ 0.75

mg/m²/day dexamethasone or equivalent) at time of enrollment. However, patients who require intermittent use of bronchodilators or local steroid injections will not be excluded from the study.

3.3. Screening and Study Enrollment Procedures

The NFCTC Operations Center should be contacted to ensure availability of a treatment slot for this research. Contact the center at [contact].

3.3.1. Informed Consent/Accent

The investigational nature and objectives of the trial, the procedures and treatments involved and their attendant risks and discomforts, and potential alternative therapies will be carefully explained to the patient or the patient's parent(s) or guardian if the patient is a child. When appropriate, pediatric patients will be included in all discussions. All patients and/or their parents or legally authorized representatives must sign a written informed consent to participate in this research. Assent, when appropriate, will be obtained according to institutional guidelines.

- A study participant should sign the institution's Release of Medical Information Waiver if applicable.

3.3.2. Screening Procedures

Diagnostic or laboratory studies performed exclusively to determine eligibility for this trial must only be done after obtaining written informed consent. Documentation of the informed consent for screening will be maintained in the participant's research chart. Studies or procedures that were performed for clinical indications (not exclusively to determine eligibility) may be used for baseline values even if the studies were done before informed consent was obtained. See section 3.4.

Before the patient can be enrolled, the responsible institutional investigator must sign and date the completed eligibility checklist. The completed eligibility checklist and redacted supporting source documents should be scanned and emailed to the NFCTC Operations Center to confirm eligibility prior to participant enrollment. Email: [contact].

3.3.3. Study Enrollment

Patients may be enrolled on the study once all eligibility requirements for the study have been met, and a treatment number for participant has been confirmed by the NFCTC Operations Center. All patients who give informed consent for the protocol in order to undergo screening for eligibility will be registered but are not considered enrolled until the screening is completed, they are determined to meet all eligibility criteria, and approval for enrollment has been confirmed by the study chair. Treatment must start within 7 days of enrollment. **Participants must not receive any protocol therapy prior to enrollment.**

3.4. Requirements to Initiate Protocol Therapy

All studies to determine eligibility must be performed within 2 weeks (14 days) prior to enrollment except the baseline MRI study and eye exam for OPG documenting disease status, which must be obtained within 4 weeks (28 days) prior to study enrollment and starting treatment. All clinical and laboratory data required for determining eligibility of a participant enrolled on this trial must be

available in the participant's medical or research record which will serve as the source document for verification at the time of audit/monitoring.

3.5. Criteria for Removal from Protocol Therapy and Off Study Criteria

Removal from Protocol Therapy

The following are criteria for removal from protocol therapy:

- a) Confirmed progressive disease (clinical or radiographic).
- b) Completion of cycle 24.
- c) Poly-ICLC related toxicity requiring removal.
- d) Participant has not received drug (for any reason) for greater than 28 days.
- e) Refusal of further protocol therapy by participant/parent/guardian.
- f) Another tumor develops that requires non-surgical therapy (e.g. chemotherapy, radiation etc;).
- g) Non-compliance, that in the opinion of the investigator does not allow for on-going participation.
- h) Physician determines it is not in the participant's best interest.
- i) Participant has complete resection of target lesion and there is no evidence of residual disease.
- j) Participant becomes pregnant.
 - If a participant becomes pregnant while receiving investigational therapy or within 90 days after the last dose of study drug, the participant should be followed until the outcome of the pregnancy.

Participants who are off protocol therapy are to be followed until they meet the criteria for OFF Study (see below).

Off-Study Criteria:

- Completion of their 5 year follow-up MRI scan
- Participant starts new tumor-directed therapy
- Death
- Lost to follow-up
- Withdrawal of consent for any further data submission

4. TREATMENT PLAN

4.1. Study Treatment

Overview:

Enrolled participants will receive poly-ICLC 20 mcg/kg/dose twice weekly IM (using Monday/Thursday or Tuesday/Friday schedule if possible). The first dose will be administered in the clinic under supervision of a nurse, advance care provider or physician. **It is recommended that the participant stay in the clinic for the 1st hour (+/- 30 min) after first dose is administered to evaluate for fever, rash, hives, or any other reactions.** Premedication with acetaminophen, ibuprofen and antihistamines is strongly recommended to minimize injection related and drug related toxicities. Prophylaxis with acetaminophen and/or ibuprofen is recommended for 24 hours after injection, per treating physician discretion.

4.2. Treatment Dosing Options

Table 4: Recommended Dosing Options

	Option 1*	Option 2*
Monday	X	
Tuesday		X
Wednesday		
Thursday	X	
Friday		X
Saturday		
Sunday		

X= drug administration. Cycles are 28 days

*If a participant misses a dose of medication on the scheduled day, a dose can be given up to 24 hours later. Injections must be separated by at least 48 hours.

Participants will receive poly-ICLC 20 mcg/kg/dose twice weekly IM (using Monday/Thursday or Tuesday/Friday schedule if possible). The first dose will be administered in the clinic under supervision. To facilitate processing of biological samples, samples should not be obtained on a Friday.

Participant will be monitored 1 hour (+/- 30 minutes) after the first dose. For all subsequent cycle 1 doses administered at home, a log will be kept documenting the temperature of the participant before study drug administration and 12 hours (+/- 6 hours) after study drug administration. After cycle 1, temperature will only be monitored on an as needed basis, such as if the participant is not feeling well. Participants or their parents will be instructed to use a log to record the temperature monitored at home and any fever > 39⁰ Celsius should be recorded on the log.

Participant or parent will receive appropriate teaching by the medical team for intramuscular injections administration. After the first dose if family and medical team feel comfortable, then the rest of the medication will be administered at home. The study drug will be dispensed to the participant/parent/guardian by the institutional research pharmacy. The study drug will be dispensed in vials along with syringes in order to minimize errors in dosing. Needle size/gauge to be used for IM injections should follow institutional guidelines and practice.

Total length of treatment will be 24 cycles. Each cycle will be 28 days +/- 5 days. Treatment will not be continued beyond 24 cycles.

Participants will be seen and monitored at the start of each cycle. A medication supply for up to a maximum of 33 days (28 + 5 days) will be dispensed.

If a participant misses a dose of medication on the scheduled day, a dose can be given up to 24 hours later. No injections should be given closer than 48 hours.

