6.6. Toxicity

See the current Investigator's Brochure for a complete list of expected toxicities.

1. Discomfort at IM injection site: The most common adverse effect is mild, transient discomfort at the site of IM injection. With subcutaneous (SC) injections, there is a transient mild to moderate grade 1 or 2 erythematous skin reaction.³

2. Flu-like symptoms: Approximately 8 to 12 hours after doses of 10 to 50 mcg/kg IM, patients may develop a mild flu-like syndrome with fever of less than 39 °C, which may last for about 12 hours, but responds readily to acetaminophen or ibuprofen. Mild myalgia, arthralgia, sometimes nausea, and malaise can be present during this period. This flu-like syndrome typically diminishes markedly after the first few poly-ICLC treatments. On rare occasions in the course of treatment, patients who have been tolerating treatment uneventfully may develop an earlier, more pronounced fever with chills and malaise (typical of higher dose IV poly-ICLC) in response to an IM injection. This will typically resolve over 12 to 24 hours, responds to acetaminophen, and does not typically recur on subsequent dosing.

3. Hematologic abnormalities: Several cases of transient leukopenia have been reported at higher doses. High dose Poly-ICLC has been associated with a coagulopathy in dogs, but not in other species including primates. There has been no change in the expected incidence of deep venous thrombosis, pulmonary embolus, or coagulopathy in multiple sclerosis, AIDS or malignant glioma patients on low dose IM poly-ICLC. One paralyzed multiple sclerosis patient treated with 100 mcg/kg IV suffered a fatal pulmonary embolus, which was not judged to be due to the drug.

4. Hepatic enzyme elevation: Mild and typically transient hepatic enzyme elevation has been described in poly-ICLC when given intravenously at doses from 20 to 100 mcg/kg. Preclinical studies have shown increased hepatic NK cells, as well as suppression of the P450 hepatic enzyme system by poly-ICLC, but the clinical implications of this finding are not clear.

5. Seizures: Seizures during high febrile episodes have been reported with glioma and known seizure disorder.

6. Diarrhea: Grade 1-2 diarrhea has been reported in brain tumor patients receiving IM Poly-ICLC two to three times weekly for months.

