Based on the safety analysis set, information regarding study treatment administration, drug dosing and cycle compliance, safety variables, will be described and summarized. Data from the biological analysis will also be described and summarized. Safety will be assessed via tabulations of AEs and SAEs as well as Diary recordings following treatment dose/cycle of therapy.

All analyses for outcome results will be based on evaluable participants, as defined in section 14.

At the end of the trial, we will report poor performance if the treatment is rejected when not meeting the criteria of at least 3 responders' cases. If there is no success, we will report a failure to reject the null hypothesis. If the null hypothesis is rejected, the probability of the estimated success rate will be reported and 95% confidence intervals as well as the distribution of changes in tumor size.

Dose-limiting toxicity (DLT) is not an objective in this trial. Toxicity will be continuously monitored.

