APPENDIX 8: Poly-ICLC Diaries

Cycle 1: Monday/Thursday Dosing

Cycle 1: Tuesday/Friday Dosing

Cycle __: Monday/Thursday Dosing

Cycle __: Tuesday/Friday Dosing

A: NF Protocol 111 Medication Diary Cycle 1

Monday/Thursday Dosing

Patient Initials _____

PID# _____

Administer Poly-ICLC as an intramuscular injection two days a week on Mondays and Thursdays. Each dose must be given at least 2 days apart. If a dose is missed, it may be given within 24 hours of when the initial dose is due. After 8 doses, do not administer any more doses until you return to clinic.

Write down the date, time, and site of administration of Poly-ICLC. For Cycle 1 record the temperature prior to each dose and 12 hours (+/- 6 hours) after each dose. After Cycle 1 temperature is only monitored on an as needed basis (if patient is not feeling well), and should be recorded if greater than 102.2° Fahrenheit (39.0° Celsius).

	Date	Time	Site of Administration	Temperature	Other Problems
Week 1 Dose 1 (Monday)				Pre-Dose Temp _____ Time _____ 12 Hour Temp _____ Time _____	
Week 1 Dose 2 (Thursday)				Pre-Dose Temp _____ Time _____ 12 Hour Temp _____ Time _____	
Week 2 Dose 1 (Monday)				Pre-Dose Temp _____ Time _____ 12 Hour Temp _____ Time _____	
Week 2 Dose 2 (Thursday)				Pre-Dose Temp _____ Time _____ 12 Hour Temp _____ Time _____	
Week 3 Dose 1 (Monday)				Pre-Dose Temp _____ Time _____ 12 Hour Temp _____ Time _____	
Week 3 Dose 2 (Thursday)				Pre-Dose Temp _____ Time _____ 12 Hour Temp _____ Time _____	
Week 4 Dose 1 (Monday)				Pre-Dose Temp _____ Time _____ 12 Hour Temp _____ Time _____	
Week 4 Dose 2 (Thursday)				Pre-Dose Temp _____ Time _____ 12 Hour Temp _____ Time _____	

B: NF Protocol 111 Medication Diary Cycle 1

Tuesday/Friday Dosing

Patient Initials _____

PID# _____

Administer Poly-ICLC as an intramuscular injection two days a week on Mondays and Thursdays. Each dose must be given at least 2 days apart. If a dose is missed, it may be given within 24 hours of when the initial dose is due. After 8 doses, do not administer any more doses until you return to clinic.

Write down the date, time, and site of administration of Poly-ICLC. For Cycle 1 record the temperature prior to each dose and 12 hours (+/- 6 hours) after each dose. After Cycle 1 temperature is only monitored on an as needed basis (if patient is not feeling well), and should be recorded if greater than 102.2° Fahrenheit (39.0° Celsius).

	Date	Time	Site of Administration	Temperature	Other Problems

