Week 1 Dose 1 (Tuesday)				Pre-Dose Temp _____ Time _____ 12 Hour Temp _____ Time _____	
Week 1 Dose 2 (Friday)				Pre-Dose Temp _____ Time _____ 12 Hour Temp _____ Time _____	
Week 2 Dose 1 (Tuesday)				Pre-Dose Temp _____ Time _____ 12 Hour Temp _____ Time _____	
Week 2 Dose 2 (Friday)				Pre-Dose Temp _____ Time _____ 12 Hour Temp _____ Time _____	
Week 3 Dose 1 (Tuesday)				Pre-Dose Temp _____ Time _____ 12 Hour Temp _____ Time _____	
Week 3 Dose 2 (Friday)				Pre-Dose Temp _____ Time _____ 12 Hour Temp _____ Time _____	
Week 4 Dose 1 (Tuesday)				Pre-Dose Temp _____ Time _____ 12 Hour Temp _____ Time _____	
Week 4 Dose 2 (Friday)				Pre-Dose Temp _____ Time _____ 12 Hour Temp _____ Time _____	

C: NF Protocol 111 Medication Diary Cycle _____
Monday/Thursday Dosing

Patient Initials _____
PID# _____

Administer Poly-ICLC as an intramuscular injection two days a week on Mondays and Thursdays. Each dose must be given at least 2 days apart. If a dose is missed, it may be given within 24 hours of when the initial dose is due. After 8 doses, do not administer any more doses until you return to clinic.

Write down the date, time, and site of administration of Poly-ICLC. For Cycle 1 record the temperature prior to each dose and 12 hours (+/- 6 hours) after each dose. After Cycle 1 temperature is only monitored on an as needed basis (if patient is not feeling well), and should be recorded if greater than 102.2° Fahrenheit (39.0° Celsius).

	Date	Time	Site of Administration	Temperature (after Cycle 1 only required if patient not feeling well)	Other Problems
Week 1 Dose 1 (Monday)					
Week 1 Dose 2 (Thursday)					
Week 2 Dose 1 (Monday)					
Week 2 Dose 2 (Thursday)					
Week 3 Dose 1 (Monday)					
Week 3 Dose 2 (Thursday)					
Week 4 Dose 1 (Monday)					
Week 4 Dose 2 (Thursday)					

D: NF Protocol 111 Medication Diary Cycle _____
Tuesday/Friday Dosing

Patient Initials _____
PID# _____

Administer Poly-ICLC as an intramuscular injection two days a week on Mondays and Thursdays. Each dose must be given at least 2 days apart. If a dose is missed, it may be given within 24 hours of when the initial dose is due. After 8 doses, do not administer any more doses until you return to clinic.

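### After cycle 1 the diary stops scheduling temperatures and asks for them only above 39.0 °C, so tabulated diary fever would fall partly or largely because the recording rule changes

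*Combined protocol and SAP*

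**What the plan says.** **Cycle 1.** For home doses, section 4.2 states that "a log will be kept documenting the temperature of the participant before study drug administration and 12 hours (+/- 6 hours) after" each dose. The Appendix 8 diary extends this to all eight doses: "For Cycle 1 record the temperature prior to each dose and 12 hours (+/- 6 hours) after each dose". Neither sets a threshold for these readings.

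**After cycle 1.** Section 4.2: "After cycle 1, temperature will only be monitored on an as needed basis, such as if the participant is not feeling well". The diary instruction adds that a temperature "should be recorded if greater than 102.2° Fahrenheit (39.0° Celsius". Two other places are looser. Section 4.2 tells families to log temperatures monitored at home and also any fever above 39 °C. The temperature column in diaries C and D, used from cycle 2, says "after Cycle 1 only required if patient not feeling well" and gives no cut-off.

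**Expected reaction.** Section 6.6 says that about 8 to 12 hours after a dose "patients may develop a mild flu-like syndrome with fever of less than 39" °C. It adds that the syndrome usually lessens markedly after the first few treatments.

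**Analysis.** Section 14.3: "Safety will be assessed via tabulations of AEs and SAEs as well as Diary recordings following treatment dose/cycle of therapy". It does not mention that the collection rule changes after cycle 1, and it gives no denominator of doses with a measured temperature.

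**The concern.** Two things change together at the end of cycle 1. Measurement goes from scheduled to symptom-triggered, and on the diary's wording a recording threshold appears that lies above the fever the protocol expects. A fever of 38.5 °C would be entered in cycle 1. In cycle 5 it might not be measured, and if measured, the diary instruction does not ask for it.

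A table of diary recordings by cycle would therefore tend to show less fever after cycle 1 whether or not tolerance develops. Because section 6.6 already predicts a decline, such a table could be taken as confirming it, when the data cannot separate a true decline from a change in recording. Toxicity is a secondary objective, and section 2.3 reports that patients with NF1-associated tumors had more side effects, fever in particular, so the later course of fever is a question readers will ask.

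**Working it through.** The plan states no figure on this point, so there is nothing to reproduce. The check counts coverage and then asks how large the artefact could be.

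**Coverage**
- Doses per cycle: 8 (Appendix 8). Cycles: 24 (section 4.2). Planned doses: 8 × 24 = 192.
- Doses with scheduled temperatures: 8, so 8 / 192 = 4.2%. On section 4.2 alone the cycle 1 log covers home doses; if only the first dose is given in clinic, that is 7 / 192 = 3.6%.
- Doses without a scheduled temperature: 192 − 8 = 184 per participant, or 184 × 20 = 3,680 at the maximum enrolment of 20 (section 14.2).
- Vital signs at the visit opening each cycle (section 5.2) are not timed to the 8 to 12 hours after a dose when section 6.6 expects the reaction.

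**Size of the artefact if the true fever rate never changes**

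Let f be the true fever rate per dose, s the share of fevers above 39 °C, and u the probability that a fever after cycle 1 is measured at all. The documents give none of these, so the values are assumptions: s from 0 to 30% and u from 0.25 to 1.0. Cycle 1 readings are taken to catch every fever, and u is taken as the same for high and low fevers.

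- Cycle 1 logged rate: f
- Later rate, diary's 39 °C rule: f × s × u, so the apparent fall is 1 − s × u
- Later rate, every measured fever logged: f × u, so the apparent fall is 1 − u

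The true rate f cancels.

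| u | 39 °C rule, s = 0 | 39 °C rule, s = 10% | 39 °C rule, s = 30% | Every measured fever logged |
|---|---|---|---|---|
| 1.00 | 100% | 90% | 70% | 0% |
| 0.75 | 100% | 92.5% | 77.5% | 25% |
| 0.50 | 100% | 95% | 85% | 50% |
| 0.25 | 100% | 97.5% | 92.5% | 75% |

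Example: s = 10% and u = 0.5 give 1 − 0.10 × 0.5 = 95% under the 39 °C rule and 1 − 0.5 = 50% otherwise.

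Two simplifications matter. If the single reading at 12 ± 6 hours misses some cycle 1 fevers, the apparent fall is smaller. If higher fevers are more likely to be measured, the 39 °C columns are governed by the higher u that applies to those fevers.

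**The case against.** **The 39 °C limit is not stated consistently.** No passage says that lower temperatures must be left out. Section 4.2 and the column heading in diaries C and D can be read as logging whatever is measured. This stands. A reader might infer that fever vanishes from the diary by construction, but that needs both the strict reading and no fever above 39 °C. Section 6.6 itself describes rare, more pronounced later fevers with chills and malaise, which would prompt a measurement. On the looser reading the fall is 0% to 75%, and it is zero if every fever is measured.

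**No comparison between cycles is planned.** In section 14.3 the wording may mean only recordings made after dosing, and the section calls its analyses largely descriptive. This also stands: a test of trend or a claim of tolerance cannot be read into the plan. But the text ties diary recordings to dose and cycle, and a descriptive table laid out that way invites the comparison.

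**Toxicity does not rest on the diary.** The secondary endpoint is the grade and duration of CTCAE toxicities (section 14). All observed or volunteered adverse events are recorded, without a temperature cut-off (section 11.4). The log is reviewed at every visit (section 5.2), and PRO-CTCAE is collected at several time points (section 8.1). A reader might infer that the toxicity endpoint is compromised; these routes show otherwise. What remains is that a fever nobody measured is missing as a measured fever there too, and that the diary tabulation is an output of its own.

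**Blood counts.** A reader might extend the argument to CBCs, which are also scheduled more densely in cycle 1, and ask for by-cycle tables from day 1 counts only. The documents do not support that. CBCs are not diary data, and the cycle 1 day 1 count is required only if none was done within 14 days (section 5.2), so it is a pre-treatment value. Using it alone would discard the on-treatment counts of days 8 and 15. The point is confined to temperature.

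**Conclusion.** The point holds for the diary tabulation. Scheduled temperatures cover 4.2% of planned doses, all in cycle 1; from cycle 2 measurement is symptom-triggered, and section 14.3 does not say so. With a constant true rate, diary fever would appear to fall by about 70% to 100% under the diary's 39 °C instruction, or by 0% to 75% if every measured fever is logged. The coverage count comes from the documents; the percentages rest on the assumed s and u and show what could happen, not what will. Which range applies depends on passages that conflict and must be reconciled.

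The consequence is limited. The primary endpoint and the Grade 4 safety rule in section 12 are untouched, and adverse event reporting continues throughout. It is still worth correcting, because the artefact runs in the direction the protocol already expects and is nearly free to remove.

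**What to change.** 1. **Section 4.2 and diaries C and D.** Replace the instruction to record temperatures above 39.0 °C with one asking families to write down every temperature they take after cycle 1, whatever its value, with date and time. Align the column heading. The same sentence is printed in diaries A and B and should be changed with it.
2. **Section 14.3.** Present diary fever for cycle 1 separately from later cycles. For each cycle, give the number of doses with a measured temperature beside the number of fevers. State that diary fever is not compared between cycle 1 and later cycles because the collection rule changes. Keep reporting later-cycle diary fevers; they remain useful safety information.

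The cost is one diary sentence, a short addition to the analysis text and slightly more diary entry for families. No visit or required measurement is added. The price is that no diary-based fever trend running from cycle 1 onward can be claimed, and the present design could not support one.
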